#### 6.5.3.1. Additional Safety Analyses

#### 6.5.3.1.1. Ophthalmological Examination

Ophthalmological examination will be performed at screening (within 28 days prior to study medication administration on Day 1 of Cycle 1), 4-6 weeks after starting treatment with TAS-120, End of treatment visit, and 30-day safety follow-up. Ophthalmological examination results will be summarized and listed.

#### 6.5.3.1.2. Neurological Examination

The neurological examination will be obtained at screening within 28 days prior to TAS-120 administration on Day 1 of cycle 1, other time due to local requirements or physician judgement, end of treatment visit, and 30-day safety follow-up visit. The examination results will be listed.

#### 6.5.4. Vital Signs

Vital sign measurements including systolic blood pressure, diastolic blood pressure, pulse rate, respiration rate, and temperature at each scheduled and changes from baseline in vital sign measurements will be summarized with descriptive statistics at each scheduled time point.

Weight at each scheduled time and changes from baseline will be summarized with descriptive statistics at each scheduled time point for the safety population. Weight will be displayed in kilograms, height, collected only at baseline, will be displayed in centimeters, and temperature will be displayed in Celsius. The safety population will be used.

All vital signs data will be presented in a listing.

#### 6.5.5. Electrocardiograms

The results of the read 12-lead ECG at each scheduled will be summarized by the categories Normal; Abnormal, not clinically significant; and Abnormal, clinical significant. If two ECG measurements are collected during one visit, the worst category will be used in the summary. The safety population will be used.

A summary of interval duration measurements at each cycle and change from baseline will be summarized with descriptive statistics at each scheduled time point. QTcF result values will be categorized as follows: <=470 msec, >470 and <=480 msec, >480 and <=500 msec, >500 msec. A summary of the frequency of QTcF interval result and change from baseline categories will be generated by visit. The change from baseline categories defined as: QTc interval increase from baseline <= 30 msec; QTC interval increases from baseline 30 - 60 msec; QTc interval increases from baseline > 60 msec: If two ECG measurements are collected during one visit, the mean measurement will be used in the summary.

The 12-lead, resting ECGs will be obtained to explore the relationship between the plasma concentration of TAS-120 and QTc prolongation.

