Cardiac	If at any time a QTcF > 480 ms and ≤ 500 ms is observed, a cardiology consultation must be sought to re-evaluate the abnormal ECG finding. If at any time a QTcF > 500 ms is observed, 1) Triplicate ECGs (2-3 minutes apart) need to be taken approximately 1 hour after the initial ECG. 2) If the mean QTcF is > 500 ms, the patient must postpone study treatment until a cardiologist has re-evaluated the ECG. 3) The re-evaluation of ECG needs to be done as soon as practical but within 7 days of the initial abnormal ECG. 4) If the cardiologist confirms a mean QTcF > 500 ms, the patient must be discontinued permanently from study.
Non-laboratory	Patients who experience non-laboratory Grade 3 or 4 AEs must be evaluated at least once a week following demonstration of the resolution of the toxicity to allow for re-treatment, until stabilization of the toxicity, or until study completion.

Abbreviations: AE = adverse event; ALT = alanine aminotransferase; AST = aspartate aminotransferase
CTCAE = Common Terminology Criteria for Adverse Events; ECG = electrocardiogram; ms = milliseconds;
QTcF = Fridericia's corrected QT interval; ULN = upper limit of normal

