# **6.5.5.** Electrocardiograms

Descriptive statistics for ECG parameters and changes from baseline will be presented by visit and treatment group (and/or dose).

Shift tables will present changes from baseline in ECG interpretation (categorized as normal; abnormal, not clinically significant; and abnormal, clinically significant) to end of treatment (or end of phase or by visit).

In addition, the number (percentage) of patients with at least 1 post-baseline abnormal ECG result in QTc Fridericia during the on-treatment period will be summarized. Clinically abnormal ECG results based on QTc Fridericia correction will be categorized as follows:

Absolute QTcF interval prolongation:

- QTc interval <= 470 ms
- QTc interval >470 480 ms
- QTc interval > 480 500 ms
- QTc interval > 500 ms

Change from baseline in QTcF interval:

- QTC interval increases from baseline <= 30 ms
- QTC interval increases from baseline 30 60 ms
- QTC interval increases from baseline > 60 ms

The number patient who experienced QTc abnormalities during the post baseline, but not presented in the baseline measurements will be summarized.

A subject level listing of ECG will be provided.

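### The Phase 1 Expansion SAP reports QTcF categories only by visit, averages two ECGs at a visit and has no per-patient worst value, so its QTcF table may under-report prolongation

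*SAP*

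**What the plan says.** The Phase 1 Expansion SAP, section 6.5.5, sets the bands: "QTcF result values will be categorized as follows: <=470 msec, >470 and <=480 msec, >480 and <=500 msec, >500 msec". Change from baseline is banded at 30 and 60 ms. The unit of tabulation is the visit: "A summary of the frequency of QTcF interval result and change from baseline categories will be generated by visit". For repeats, "If two ECG measurements are collected during one visit, the mean measurement will be used in the summary". The same section treats the normal/abnormal interpretation the other way: "If two ECG measurements are collected during one visit, the worst category will be used in the summary". It contains no per-patient maximum and no rule for unscheduled ECGs.

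The protocol's ECG schedule (section 9.7) has one ECG at each time point. Repeats come from the cardiac row of Table 9 (section 8.1.3.1.2). The trigger is "If at any time a QTcF > 500 ms is observed", and then "Triplicate ECGs (2-3 minutes apart) need to be taken approximately 1 hour after the initial ECG". The next step depends on a mean: "If the mean QTcF is > 500 ms, the patient must postpone study treatment until a cardiologist has re-evaluated the ECG".

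The other parts of the study count patients. The Phase 2 SAP, section 6.5.5, plans that the number of "patients with at least 1 post-baseline abnormal ECG result in QTc Fridericia during the on-treatment period will be summarized". The Dose Escalation SAP, section 10.6, counts patients per QT/QTc category by dose level and overall. For laboratory grades, section 6.5.3 of the Expansion SAP itself takes the worst post-baseline grade and includes unscheduled visits.

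**The concern.** A mean suits replicates planned in advance, because it reduces measurement noise without favouring either direction. The repeats in Table 9 are different: they exist because one reading was above 500 ms. Averaging a reading selected for being extreme with later readings will tend to pull the visit value down, possibly out of the top category.

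The by-visit layout is a separate problem. The usual safety question is how many patients ever exceeded 500 ms, or ever rose more than 60 ms from baseline. Counts at each visit do not show whether the same patient or different patients are involved. The Expansion part plans about 185 patients, and the protocol both screens for QT prolongation (QTcF above 470 ms is an exclusion criterion) and manages it. As planned, its QTcF table could not be set beside the patient counts from the other two parts.

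**Working it through.** The documents state no figure to reproduce, so this is arithmetic on the averaging rule.

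**Inputs.** The threshold is 500 ms (Expansion SAP 6.5.5; protocol Table 9). The rule as written covers two ECGs. The Table 9 trigger yields four: the initial reading x0 and a triplicate with mean m. The values of x0 and of the repeats below are illustrative.

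**Step 1: initial reading plus one repeat r.** The visit mean is (x0 + r)/2, which is at or below 500 when r ≤ 1000 − x0.

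**Step 2: initial reading plus triplicate, if all four were averaged.** The visit mean is (x0 + 3m)/4, which is at or below 500 when m ≤ (2000 − x0)/3.

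| x0 (ms) | One repeat: leaves the >500 band if r ≤ | Four ECGs: leaves the >500 band if m ≤ |
|---|---|---|
| 510 | 490 | 496.7 |
| 520 | 480 | 493.3 |
| 540 | 460 | 486.7 |

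For example, with x0 = 510 and one repeat of 480, (510 + 480)/2 = 495.0. With x0 = 510 and m = 480, (510 + 1440)/4 = 487.5. Both fall in the >480 to 500 band.

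**Step 3: what happens to confirmed excursions.** If x0 > 500 and m > 500, then (x0 + 3m)/4 > 500. A four-ECG mean therefore never removes an excursion that the triplicate mean confirms. All the four-ECG limits in the table are triplicate means below 500, so they describe unconfirmed readings.

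**Step 4: how often this could happen (illustration only).** None of these values is in the documents: mean QTcF 430 or 450 ms, between-patient SD 25 ms, within-visit SD 5, 10 or 15 ms, and every initial reading above 500 ms followed by a triplicate. In simulation, 19% to 69% of initial readings above 500 ms had a four-ECG mean at or below 500, and 15% to 55% had a mean at or below 500 when paired with one repeat. Confirmed readings lost were 0% with the four-ECG mean, and about 2% to 3% of initial readings above 500 ms with the pair.

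**Step 5: by-visit counts against ever-exceeded counts.** Suppose 1% of patients exceed 500 ms at each of 10 visits. If they are the same patients each time, 1% ever exceed it. If visits are independent, the figure is 1 − 0.99^10 = 9.6%. If they are different patients each time, it is 10 × 1% = 10%. The by-visit table is the same in all three cases.

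**The case against.** A reader might infer that the SAP averages the triggered ECGs together, that a reading above 500 ms at an unscheduled visit is never counted, and that QT prolongation is therefore under-reported. The documents do not support that much.

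- The mean rule names two ECGs and the trigger yields four. The SAP is silent on how those four are combined.
- Table 9 itself acts on a mean. By step 3, an excursion confirmed by the triplicate mean stays above 500 ms in a four-ECG average. In the four-ECG cases tabulated above, the condition for postponing treatment is not met, and what the protocol requires is the repeat ECGs.
- Unscheduled ECGs are not expressly excluded. In section 6.5.5 the restriction to scheduled time points is attached to the interpretation summary and the descriptive statistics. The QTcF category table is simply by visit.
- Part of the signal appears elsewhere: the interpretation table uses the worst category, all relevant data go into patient listings (Expansion SAP 6.1), and an ECG abnormality with clinical impact is an adverse event (protocol 11.1.1).
- Protocol section 12.2.3 centres safety evaluation on adverse events and laboratory results and prescribes no QTcF table, so nothing in the protocol is breached. Separate SAPs may use different displays.

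These points limit the size of the problem but do not remove it. The interpretation table carries no millisecond threshold. A reading whose triplicate mean is 500 ms or less does not require postponement under Table 9 and may never be recorded as an adverse event; those are the readings a mean tends to remove. A listing holds the values but is not an incidence. No planned table gives a per-patient worst QTcF.

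**Conclusion.** The point holds in a limited form. The Expansion QTcF summary may under-report prolongation, because averaging can move an observed reading above 500 ms into a lower band and because by-visit counts cannot give the proportion of patients ever above 500 ms. The two-ECG case (510 and 480 giving 495 ms) follows directly from the stated rule. The 496.7 ms limit rests on the assumption that all four ECGs are averaged, which the SAP does not say. The loss falls mainly on readings the triplicate did not confirm. The simulated percentages depend on assumed means and SDs and show a possible range, not an expected rate. It remains unstated how the initial ECG and triplicate are combined and where unscheduled ECGs go. No primary endpoint depends on this table. The correction is still worth making, since the data are already collected and the other two SAPs count patients.

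**What to change.** Add to Expansion SAP 6.5.5 the number and percentage of patients by maximum post-baseline QTcF (≤470, >470 to 480, >480 to 500, >500 ms) and by maximum increase from baseline (≤30, >30 to 60, >60 ms). Use every on-treatment ECG, including unscheduled and triggered ones. Do not average a triggering reading with its repeats, and show the triplicate mean alongside so that confirmed and unconfirmed excursions can be told apart. The by-visit table can stay, with a sentence saying how the initial ECG and the triplicate enter it.

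This follows the patient-level approach of the Phase 2 SAP and goes further, since that SAP specifies neither the maximum nor the use of unscheduled ECGs. The cost is one extra table and possibly slightly less favourable QTcF rates. The protocol's clinical QTc rule is not affected.

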#### 6.5.6. Physical Examination

All physical examination will be performed 24 hours prior to TAS-120 administration on day 1 beginning with cycle 2. The baseline screening measurement of physical examination will be taken on screening within 28 days prior to TAS-120 administration on Day 1 of Cycle 1. The physical examination will also obtain at the End of Treatment Administration, and 30-day safety follow-up visit.

The physical examination data will be presented in a patient level listing.

#### **6.5.7. ECOG Performance Status**

The ECOG performance status score will be obtained at the following time points: screening, and 24 hours prior to TAS-120 on day 1 beginning with cycle 2, the End of Treatment Administration, and 30-day safety follow-up visit. The ECOG performance status scores and the grades from 0 to 5 is described in the following table:

Table 10. Grade Categories of Eastern Cooperative Oncology Group Score

GRADE	ECOG
0	Fully active, able to carry on all pre-disease performance without restriction.
1	Restricted in physically strenuous activity but ambulatory and able to carry out work of a light or sedentary nature, eg, light house work, office work.
2	Ambulatory and capable of all self-care but unable to carry out any work activities. Up and about more than 50% of waking hours.
3	Capable of only limited self-care, confined to bed or chair more than 50% of waking hours.
4	Completely disabled. Cannot carry on any self-care. Totally confined to bed or chair.
5	Dead.

The change from Day 1 in Cycle 1 in the ECOG performance status scores will be presented in a shift table. A patient level listing will also presented.

#### 6.5.8. Pregnancy Test

If the patient is female and of child bearing potential, a serum or urine beta-human chorionic gonadotropin ( $\beta$ -HCG) pregnancy test will be performed 7 days prior to the first administration of the study drug. Pregnancy test result will be listed.

## 6.6. Other Analyses

The Quality of Life data is not collected in the Phase I Expansion study.

### 6.8. Pharmacokinetic Analyses

#### 6.8.1. Optional Pharmacokinetic Samples

Optional blood PK samples will be collected per the investigator's discretion in any patient at the following time points: prior to dosing (0 hour) and post-dose at 1, 2, 3, 4, 6, and 24 hours ( $\pm$  10 minutes). The 24-hour post-dose sample should be collected prior to next TAS-120 administration. These optional blood PK samples could be collected on any day in Cycle 1 and Cycle 2 when PK should be collected as part of the safety evaluation.

For patients in the Phase I Expansion with primary CNS tumors only, optional blood and CSF samples will be collected 2-4 hours post-dose on Day 1 of Cycle 2 to assess the TAS-120 concentration ratio of CSF to plasma. Blood and CSF samples must be collected at the same time point (within 15 minutes).

Kp (TAS-120 concentration ratio of CSF to plasma) will be calculated as follows:

Kp = CSF concentration / Plasma concentration at the same time.

For patients whose CSF sample was collected, the summary Table for plasma and CSF concentrations and Kp value will be provided.

A patient level listing for plasma, CSF concentrations and Kp values will be provided.

#### **6.8.2.** Pharmacokinetic Blood Samples

Blood samples of TAS-120 will be collected on Day 1 of Cycle 2 pre-dose, 1 h  $\pm$  30 min. and 3 h  $\pm$  30 min. post-dose to assess the plasma exposure at 20 mg QD. In addition, blood samples will be collected on Day 1 of Cycle 3 and Cycle 4 pre-dose.

A summary table and subject level listing for plasma concentration will be provided.

## 7. CHANGES IN PLANNED ANALYSIS

The following table summarizes substantive changes made to the SAP in the current Amendment 1;

Section	Description of Change	Brief Rationale
Section 4.1	Text was amended as follows:	In order to be consistent with the
Summary of Study Design	Group 1 (Enrollment suspended as of Amendment 7): Patients with intrahepatic or extrahepatic CCA harboring FGFR2 gene fusions or rearrangements .  Group 2: Patients with intrahepatic or	protocol.
	extrahepatic CCA harboring FGFR2 gene fusions or rearrangements that have not received or received less than 1 cycle of prior chemotherapy (due to intolerance or patient refusal)	
	Group 3 (Enrollment suspended as of Amendment 7): CCA (iCCA or eCCA) with FGFR2 gene fusions or rearrangements treated with prior FGFR inhibitors	
Section 5.4	The following text was amended as	In order to be consistent with
Timing of Analysis	follows:	patients' follow-up time.
	The final analysis will be performed when at least 90% of all treated patients had approximately 4 months of follow-up.	

#### 8. DEFINITIONS AND CONVENTIONS FOR DATA HANDLING

#### 8.1. Baseline Period

Baseline evaluations or events are defined as evaluations or events that occur before the date and time of first dose of study treatment.

If the onset time of event or evaluation time or dosing time is missing or not collected, the following definitions will be applied:

- Pre-treatment AEs will be defined as AEs with an onset date prior to but not including the day of the first dose of study treatment
- Baseline evaluations (laboratory tests, vital signs) will be defined as evaluations with a date on or prior to the day of first dose of study treatment

If there are multiple valid assessments, the assessment that is closest to day (and time if collected) prior to the first dose of study treatment will be used as the baseline in the analyses. If multiple assessments are collected at the same date (and time if collected), the assessment with the latest database entry date (and time if collected) will considered as baseline.

#### 8.2. Post-Baseline Period

On-treatment AEs will be defined as AEs with an onset date and time on or after the date-time of the first dose of study drug (or with an onset date on or after the day of first dose of study treatment if time is not collected or is missing). An AE will be counted as on-treatment if the event occurred within 30 days of the last dose of study treatment.

On-treatment evaluations (laboratory tests, vital signs) will be defined as evaluations taken after the day (and time, if collected and not missing) of first dose of study treatment. An evaluation will be counted as on-treatment if it occurred within 30 days of the last dose of study treatment.

#### 8.3. **AESI Definition and Conventions**

The AESI consist of a list of preferred terms grouped by specific category (for example, pulmonary events, gastrointestinal events categories) and/or by subcategory (for example, diabetes). These categories and subcategories are defined based on MedDRA, and the list that is most current at the time of analysis will be used. Also changes may be made to this list with each new version of MedDRA.

#### 8.4. Time-to-Onset Definition

Time-to-onset of AESI (any grade) for a specific category (for example, pulmonary events, gastrointestinal events) is defined as the time between the day of the first dose of study treatment and the onset date of the earliest AESI (of any grade) in this category.

If the subject did not experience an AESI (of any grade) in the category, time-to-onset will be censored at the maximum follow-up time of all subjects in their respective treatment group (that is, for subjects without an event, follow-up time is defined from first dosing date up to last dosing date +30 days if subjects are off treatment and followed for at least 30 days, otherwise it

is defined up to the last known alive date). The resulting Kaplan-Meier plot will represent the cumulative rate of the AESI (any grade) in the category over time.

Time-to onset of AESI (Grade 3-5) for a specific category is defined similarly but restricted to Grade 3-5 AESI.

Time-to onset of drug-related (Grade 3-5 or any grade) AESI for a specific category is defined similarly but restricted to drug-related AESI.

Time-to onset for a specific subcategory is defined similarly but restricted to events in this subcategory.

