#### 4. STUDY DESCRIPTION

#### 4.1. Summary of Study Design

This is an open-label, nonrandomized, and Phase I Expansion study of TAS-120, evaluating the efficacy, safety, and antitumor activity of the RP2D of TAS-120 in patients with advanced solid tumors with FGF/FGFR-related abnormalities who have failed all standard therapies or for whom standard therapy does not exist or is not tolerated.

As of Amendment 6, the Phase 1 Dose Escalation Phase is completed and MTD/RP2D of 20 mg QD was established.

TAS-120 will be administered orally at 20 mg, QD in 21-day cycles. Approximately 185 patients will be enrolled. Patients will be assigned to one of 8 disease groups based on diagnosis, prior therapy, and FGFR aberration:

- Group 1 (Enrollment suspended as of Amendment 7): Patients with intrahepatic or extrahepatic CCA harboring FGFR2 gene fusions or rearrangements.
- Group 2: Patients with intrahepatic or extrahepatic CCA harboring FGFR2 gene fusions or rearrangements that have not received or received less than 1 cycle of prior chemotherapy (due to intolerance or patient refusal)
- Group 3 (Enrollment suspended as of Amendment 7): CCA (iCCA or eCCA) with FGFR2 gene fusions or rearrangements treated with prior FGFR inhibitors
- Group 4 (Enrollment suspended as of Amendment 7): CCA (iCCA or eCCA) with other FGFR abnormalities, i.e., gene mutations, rearrangements or amplifications
- Group 5: Patients with primary CNS tumors harboring FGFR gene fusions or FGFR1 activating mutations
- Group 6 (Enrollment suspended as of Amendment 7): Patients with advanced urothelial carcinoma harboring FGFR3 gene fusions or FGFR3 activating mutations
- Group 7: Patients with any tumor type not included in one of the prior groups, harboring FGFR2 amplification (no minimum number of copies).
- Group 8 (Enrollment suspended as of Amendment 7): Patients with any tumor type not included in one of the prior groups, harboring FGFR gene fusions or activating mutations

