# 5. STUDY PERIODS, TREATMENT REGIMENS, AND POPULATIONS FOR ANALYSIS

#### 5.1. Study Periods

The study periods are defined in the table 4 below.

**Table 4.** Definition of Study Periods for Analysis

Period	Definition
Baseline / Screening	From the day of ICF signature (up to 28 days before first dose) to the day and time of the first dose of study drug.
On-treatment	From the date of first dose of study therapy through 30 days after the last dose of study therapy. Unless otherwise specified, the on-treatment period will be the basis for the summaries of safety.

Abbreviations: ICF=informed consent form.

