## **5.4.** Timing of Analysis

The final analysis will be performed when at least 90% of all treated patients had 4 months of follow-up.

The timing of the interim analysis please referred to Section 4.3 Determination of Sample Size of this SAP.

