#### **Time to Onset:**

Time-to-onset of selected AESI, including hyperphosphatemia, will be graphically displayed for each category/subcategory of AESI using the Kaplan-Meier technique:

• Time to AESI (grade 1 and above)

• Time to AESI of Grade  $\geq 3$ 

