#### 7.4. Time-to-Onset Definition

Time-to-onset of AESI (any grade) for a specific category (for example, pulmonary events, gastrointestinal events) is defined as the time between the day of the first dose of treatment and the onset date of the earliest AESI (of any grade) in this category.

If the subject did not experience an AESI (of any grade) in the category, time-to-onset will be censored at the maximum follow-up time of each subject in their respective treatment group (that

is, for subjects without an event, follow-up time is defined from first dosing date up to last dosing date +30 days if subjects are off treatment and followed for at least 30 days, otherwise it is defined up to the last known alive date). The resulting Kaplan-Meier plot will represent the cumulative rate of the AESI (any grade) in the category over time.

Time-to onset of AESI (Grade 3-5) for a specific category is defined similarly but restricted to Grade 3-5 AESI.

Time-to onset of study treatment-related (Grade 3-5 or any grade) AESI for a specific category is defined similarly but restricted to study treatment-related AESI.

Time-to onset for a specific subcategory is defined similarly but restricted to events in this subcategory.

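### Expansion SAP 8.4 can be read as censoring event-free patients at the group's longest follow-up; applied literally, the AESI onset curves understate later risk

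*SAP*

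**What the plan says.** Expansion SAP 8.4 measures onset from first dose to the earliest AESI in a category. For a patient with no such event, "time-to-onset will be censored at the maximum follow-up time of all subjects in their respective treatment group". A bracket in the same sentence explains that for event-free patients "follow-up time is defined from first dosing date up to last dosing date +30 days if subjects are off treatment" and they were followed for at least 30 days; otherwise follow-up runs to the date last known alive. The section then says: "The resulting Kaplan-Meier plot will represent the cumulative rate of the AESI (any grade) in the category over time". The same definition carries over to Grade 3-5, drug-related and subcategory onset.

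Expansion SAP 6.5.2.6 says that onset of selected AESIs, hyperphosphatemia among them, "will be graphically displayed for each category/subcategory of AESI using the Kaplan-Meier technique". It gives no other censoring rule. Section 7, which lists changes to that SAP, does not touch 8.4.

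Phase 2 SAP 7.4 has nearly the same sentence, but there the event-free patient is "censored at the maximum follow-up time of each subject in their respective treatment group".

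Two other provisions matter. Expansion SAP 5.1 defines the on-treatment period, the basis for safety summaries, as "From the date of first dose of study therapy through 30 days after the last dose of study therapy". Expansion SAP 5.4 sets the analysis time: "The final analysis will be performed when at least 90% of all treated patients had 4 months of follow-up". Observation therefore ends at different times for different patients.

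**The concern.** Censoring should take a patient out of the risk set when observation ends. A maximum taken over the whole group does not do that. A patient enrolled late and still on drug at month 4 would be counted as event-free until the longest follow-up in the group, although nothing is known about that patient after month 4.

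The curve is offered as the cumulative AESI rate over time. If it is low at later times, a reader sees late-onset toxicity as rarer than the data support, and the error favours the drug. Two SAPs of one trial would also define the same safety display differently.

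**Working it through.** The documents give no figure for AESI onset, so there is none to reproduce. The check is algebra, a small example and a simulation under stated assumptions.

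**1. What the literal rule does.** Kaplan-Meier gives 1 − KM(t) = 1 − ∏(1 − d_j/n_j) over event times up to t. If every event-free patient is censored at the group maximum, nobody leaves the risk set early except by having an event. Then n_j = N minus earlier events, the product telescopes, and 1 − KM(t) = (patients with an event by t)/N, the crude proportion. Each n_j is at least as large as under own-follow-up censoring, so the curve can never be higher. It is lower once an event occurs after an event-free patient's observation has ended.

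**2. Ten-patient example (invented).** Events at months 1, 4 and 8; event-free follow-up 2, 2, 3, 5, 6, 9 and 12 months.
- Own follow-up: S = 9/10 at month 1, × 5/6 = 0.75 at month 4, × 2/3 = 0.50 at month 8. Cumulative risk is 25% at month 6 and 50% at month 9.
- Group maximum: S = 9/10, × 8/9 = 0.80, × 7/8 = 0.70. Cumulative risk is 20% and 30%, that is 2/10 and 3/10.

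**3. Which patients cause real error.** Two kinds of event-free patient are kept too long.
- Those who stopped drug and completed the 30 days. An on-treatment AESI can no longer occur in them by definition. Keeping them in the denominator yields the incidence with treatment stop as a competing event, which is a legitimate target.
- Those still on treatment or within the 30 days at data cut-off. They could still have an event, so counting them as event-free is unsupported on any target.

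To confirm the first part, suppose treatment stop is the only exit. Assume constant hazard, a net 12-month risk of 40%, and exposure with median 4 months plus 1 month of follow-up. Then h = −ln(0.6)/12 = 0.0426 and d = ln(2)/4 = 0.1733 per month. Incidence by month 12 with stop as a competing event is (1 − e^(−h)) + e^(−h) × h/(h+d) × (1 − e^(−11(h+d))) = 0.042 + 0.171 = 21.3%. The crude proportion is the same 21.3%. With this exit alone the rule is unbiased for that target.

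**4. With administrative censoring.** Simulation: 100 patients, 300 replicates, exponential onset with 30% risk at 6 months, hence 1 − 0.7² = 51% net risk at 12 months. Time from first dose to data cut-off is uniform over the range shown. Treatment stop is exponential with the median shown, plus 1 month of safety follow-up. All of these inputs are assumptions. Results at month 12:

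| Median time to stop | Time to cut-off (months) | Group maximum | Aalen-Johansen, stop competing | Own-follow-up KM |
|---|---|---|---|---|
| 4 months | 4-24 | 26.5% | 28.0% | 52.0% |
| 4 months | 3-12 | 23.4% | 27.5% | 48.0% |
| 8 months | 4-24 | 33.6% | 36.3% | 50.6% |
| 8 months | 3-12 | 27.9% | 35.7% | 49.4% |
| no stopping | 4-24 | 45.5% | 50.9% | 50.9% |
| no stopping | 3-12 | 35.0% | 49.4% | 49.4% |

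Where patients stop treatment, the shortfall against Aalen-Johansen is 1.5, 4.1, 2.7 and 7.8 points. With no stopping, every early exit is administrative and the two reference curves coincide; the shortfall is 5.4 and 14.4 points.

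**5. Early times and early-onset events.** At month 3 the rule equals Aalen-Johansen in all of these settings, since no assumed cut-off comes before month 3. For an AESI with 60% susceptible and mean onset 0.5 month (assumed), with exposure as in step 3, the crude proportion is 0.6 × [1 − e^(−2) + e^(−2) × 2/(2 + 0.1733)] = 59.4%, against 60% for own-follow-up KM: under 1 point.

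**The case against.** The strongest reply is that the sentence explains itself. The bracket is introduced as a restatement, speaks only of event-free patients, and gives each one an individual end of follow-up. A programmer who applies it directly censors at own follow-up, and there is no bias. This stands as a possible reading. It does not settle the matter, because the main clause takes a maximum over all subjects and the bracket can equally be read as defining the quantity being maximised. The two readings give different curves, and the Phase 2 wording shows how the sentence can be put without the group maximum.

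A second reply is that own-follow-up Kaplan-Meier is no gold standard. It estimates the risk if nobody stopped treatment, and so overstates on-treatment incidence. This also stands. A reader who sets 23-34% against 48-52% might infer that the rule roughly halves late risk. The documents do not support that: AESIs are counted on treatment, so part of that gap is a difference in estimand. The part that is error on any target is the gap to Aalen-Johansen.

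Third, the one AESI named, hyperphosphatemia, appears to be expected early: the protocol tests phosphorus 4 days after Cycle 1 Day 1 for the sake of early intervention. For such an event the bias would be near zero.

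Fourth, the AESI incidence tables (6.5.2.6), exposure-adjusted rates (6.5.2.7) and time to resolution (8.5) do not use this rule. That is correct. Nor does either SAP set out a comparison of the Expansion and Phase 2 onset curves, so the mismatch is one of consistency rather than of a planned result.

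**Conclusion.** The concern holds as an ambiguity with a harmful literal reading. Expansion SAP 8.4 puts a group-maximum clause beside a patient-level bracket, and Phase 2 SAP 7.4 differs on exactly that point. A reader might infer that the Expansion curves are certainly biased; the text does not establish this, because the bracket permits the correct programming.

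If the clause is applied literally, the curve is the crude proportion and understates later cumulative risk for patients whose observation is ended by the data cut-off. At month 12, with an assumed net risk of 51%, it gives 23-34% against 27.5-36% by Aalen-Johansen, a shortfall of about 1.5 to 8 points when patients also stop treatment. This rests on assumed constant hazard, accrual and stopping times that are independent of AESI risk; the documents supply none of these. The shortfall grows with time and with the share of patients still under observation at cut-off. Only the time-to-onset curves are touched, including their Grade 3-5, drug-related and subcategory versions. No efficacy result depends on this rule.

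**What to change.** In Expansion SAP 8.4, replace *of all subjects* with *of each subject*, as in Phase 2 SAP 7.4. Each event-free patient is then censored at his or her own last dose + 30 days if off treatment and followed that long, and otherwise at the date last known alive. Check that the program does this, whichever way the sentence was first read.

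The cost is a two-word edit and a check, or a small change, of one derivation; no new data are needed. Late onset rates may look less favourable. Own-follow-up Kaplan-Meier also treats treatment stop and death as non-informative censoring and can overstate on-treatment incidence, so an Aalen-Johansen curve with these as competing events may be shown alongside.
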